6.2.6. Adherence Assessment CAB-LA

6.2.6.1. Adherence to the dosing schedule will be assessed at month 3 (early adherence) and end of study by:

A) Estimating the number of individuals who missed one or more consecutive injections without taking daily oral bridging PrEP while not on CAB-LA injections and mean and median number of injections missed during a 6- and a 12-month period.

6.2.7. B) Estimating the number of individuals who received the injections seven or more days later than their scheduled injection visit and the mean and median duration of delayed injections. Adherence Assessment Oral PrEP

6.2.7.1. Adherence to the dosing schedule will be assessed at months 3 (early adherence) and 12 by:

A) Estimating the number of individuals who reported three or more days of oral PrEP missed and the mean and median number of days they missed.

B) Estimating the number of individuals who had a gap of >90 days between the end of the days of supply of a dispensing and the start date of the next fill.

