6.6. PrEP Discontinuation

6.6.1. Participants will be deemed as having discontinued PrEP if they miss more than 3 consecutive months for PrEP.

6.6.2. Participants will be called, texted and emailed for three consecutive months before considered them as discontinued.

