6.13. Interventions: PrEP Initiation and Digital Health Companion Program

6.13.1. Participants will be enrolled in the CAB-LA and Oral PrEP cohorts. Participants in the CAB-LA cohort will receive their first dose of the PrEP injection at month 0. Injections will also be administered in months 1, 3, 5, 7, 9, and 11. Participants in the Oral PrEP cohort will have their prescription filled at month 0, 3, 6, 9, and 12. The schedule of dosing is presented in Figure 6a.

6.13.2. Participants in both cohorts will complete education modules and health literacy evaluations in the TheraPay App in months 2, 4, 6, 8, and 10 as presented in Figure 6a. Education Modules include PrEP Medicines (month 2), Protecting Yourself from HIV, STIs, and other infections (month 4), Building a Support System for HIV Prevention Month 6: Being an Active Participant in Your Own Care (month 8), and Overcoming Stigma and Becoming a Health Advocate (month 10).

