To assess the co-primary endpoint of persistence at 3 months and end of study, the proportion of participants reporting continued receipt of injections in the CAB-LA cohort and the proportion of patients reporting continued use of PrEP by mouth in the oral PrEP cohort on the persistence assessment will be compared using chi square tests or Fisher's exact tests. Self-reported persistence will be validated by the medication possession ratio (MPR). MPR is defined as the number of days of medication dispensed during the study period divided by the number of days that the person should have received therapy. The percent of CAB-LA participants with MPRs ≥ 1.0 will be compared to the percent of oral PrEP participants with MPRs ≥ 1.0 using chi square tests or Fisher's exact tests. To assess the co-primary endpoint of adherence, chi square tests or Fisher's

exact tests will be used to compare the percent of CAB-LA participants who reported missing one or more injections during the study period to the percent of oral PrEP participants who reported three or more missed days of oral PrEP. The percent of CAB-LA participants who received any injections seven or more days later than their scheduled injection or oral PrEP participants who had a gap of >90 days between the end of the days of supply of a dispensing and the start date of the next fill will be compared.

Sample Size

Assuming adherence proportions of .90 and .65 and sample sizes of 70 and 35 in the CAB-LA and oral PrEP arms respectively, the 95% confidence interval for the difference between the CAB-LA proportion and the oral PrEP proportion is .0771 to .4229.

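### Adherence item B compares CAB-LA injections at least 7 days late with oral refill gaps over 90 days, so the two percentages cannot be read as relative adherence

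*Combined protocol and SAP*

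**What the plan says.** Sections 6.2.6 and 6.2.7 define adherence to the dosing schedule by two items per arm.

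- **CAB-LA, item A:** participants who "missed one or more consecutive injections without taking daily oral bridging PrEP while not on CAB-LA injections".
- **CAB-LA, item B** (printed at the start of 6.2.7): participants who "received the injections seven or more days later than their scheduled injection visit".
- **Oral, item A:** self-report of at least three missed days.
- **Oral, item B:** participants with "a gap of >90 days between the end of the days of supply of a dispensing and the start date of the next fill".

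For the oral arm, 6.2.7.1 sets the timing: "Adherence to the dosing schedule will be assessed at months 3 (early adherence) and 12 by". CAB-LA is assessed at month 3 and end of study.

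Section 7 lists two between-arm comparisons for the adherence co-primary. The second takes the percentage in the CAB-LA arm counted as having "received any injections seven or more days later than their scheduled injection or oral PrEP participants who had a gap of >90 days" and says that the two will be compared. That sentence gives no time point and no test. Adherence is part of the primary objective in 3.2.1. The protocol summary, the Study Outcomes Table and the Appendix G schema do not mention item B.

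Section 6.13.1 gives the schedule. After the month-0 injection, "Injections will also be administered in months 1, 3, 5, 7, 9, and 11"; oral prescriptions are filled at months 0, 3, 6, 9 and 12. Section 6.6 states: "Participants will be deemed as having discontinued PrEP if they miss more than 3 consecutive months for PrEP".

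**The concern.** Item B applies a strict rule to one arm and a lenient rule to the other, and Section 7 then sets the results side by side. A CAB-LA participant fails on one injection a week late. An oral participant who refills anywhere from 7 to 90 days late never fails. The oral threshold is about as long as the plan's own discontinuation rule, so oral item B detects an interruption that was later resumed rather than lateness against a schedule. It also needs a next fill, so someone who stops for good is not counted by it.

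A higher CAB-LA percentage would look like worse adherence even if behaviour were the same in both arms. The study hypothesis is better adherence with CAB-LA, so the risk is a masked or reversed contrast in one of the two comparisons listed for that co-primary.

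**Working it through.** **The plan's own adherence figure.** With .90 of 70 and .65 of 35, the standard error is √(.9×.1/70 + .65×.35/35) = .0882. The interval .25 ± 1.96×.0882 is .0771 to .4229, as stated. The plan does not say which adherence item the .90 and .65 refer to, so this neither supports nor weakens the point.

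**Month 3, oral arm.** Participants are newly started on PrEP, so the first supply begins on day 0. A gap of more than 90 days can first be counted on day (days of supply + 91).

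- 90-day supply, as implied by fills every 3 months: 90 + 91 = day 181.
- 30-day supply (assumed; days of supply are not stated): 30 + 91 = day 121.

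Both fall after month 3 (about day 90-92), so the oral count is 0 of 35 whatever participants do. It could be non-zero only with very short fills, for example 31 days or less together with a month-3 cut-off read as late as about day 121-122. That does not fit the fill schedule.

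**Chances to fail by end of study.** There are six follow-up injections (months 1, 3, 5, 7, 9, 11). There are four scheduled refills (months 3, 6, 9, 12), but a delay of more than 90 days in the month-12 refill cannot be seen by month 12, which leaves three.

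**Same lateness in both arms.** Let q be the probability that a pick-up is at least 7 days late, and s the share of those that exceed 90 days. Both are assumed, and events are taken as independent.

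- CAB-LA: 1 − (1 − q)^6
- Oral: 1 − (1 − qs)^3

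| q | s | CAB-LA fails | Oral fails |
|---|---|---|---|
| .02 | .10 | 11.4% | 0.6% |
| .02 | .50 | 11.4% | 3.0% |
| .05 | .10 | 26.5% | 1.5% |
| .05 | .50 | 26.5% | 7.3% |
| .10 | .10 | 46.9% | 3.0% |
| .10 | .50 | 46.9% | 14.3% |

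Counting four refills, the oral extremes become 1 − .998^4 = 0.8% and 1 − .95^4 = 18.5%. The conclusion is unchanged.

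**What passes and what fails item B, by coverage.** Each injection is credited with the interval to the next one (assumed from the schedule).

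- Oral, 90-day fills on days 0, 180 and 360: covered 90 + 90 + 5 = 185 of 365 days (51%). Both gaps are exactly 90 days, so this participant passes.
- Oral, one 90-day fill and no return: 90/365 (25%). There is no next fill, so this participant passes.
- CAB-LA, one injection 7 days late: 358/365 (98%). This participant fails.

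**A common measure.** For proportion of days covered (PDC) to day 360, the expected difference between arms is approximately (6 − 3)×q×d/360, where d is the delay in days (assumed).

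- q = .02, d = 7: 0.42/360 = 0.1 points.
- q = .10, d = 30: 9/360 = 2.5 points.
- q = .10 with half of late pick-ups at 91 days and the rest at 7-30 days: about 3 points by simulation (roughly 92% CAB-LA, 96% oral).

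Unequal visit frequency therefore still has an effect on PDC, but a far smaller one than on item B.

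**The case against.** The strongest reply is that item B does not stand alone. Section 7 also compares self-reported persistence, and the percentage with a medication possession ratio of at least 1.0, a dispensing-based rule with one cut-off for both arms ("MPR is defined as the number of days of medication dispensed during the study period divided by the number of days" on which therapy was due). If the denominator is the study year, both oral examples above fail it: 90/365 = 0.25 and 270/365 = 0.74. This stands. It means that item B is misleading as a comparison, not that poor oral coverage goes unseen.

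A reader might infer that an oral participant who stops escapes the adherence endpoint altogether. The documents do not support that. The Appendix C persistence survey routes a participant who has stopped to the question on days missed in the past week. A stopper who answers can report 7 days and so meet oral item A. Only a stopper who does not respond is lost to it.

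A reader might infer a biased formal test at month 3. Section 7 specifies neither a time point nor a test for item B, so the claim is only that the month-3 oral figure in 6.2.7.1 carries no information.

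A reader might want to apportion the gap between thresholds and chances to fail. The split is not identified. At q = .05 and s = .50 the gap is 26.5 − 7.3 = 19.2 points. Equalising thresholds first brings oral to 1 − .95^3 = 14.3%, so unequal chances account for (26.5 − 14.3)/19.2 = 64%. Equalising chances first brings oral to 1 − .975^6 = 14.1%, so they account for (14.1 − 7.3)/19.2 = 35%.

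Finally, the bias runs against the hypothesis and might be called conservative. It cannot produce a false CAB-LA benefit, but a contrast that can reverse under identical behaviour still does not answer the question.

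**Conclusion.** The concern holds. The unequal thresholds, the need for a next fill and the comparison itself are in the text, and no other section repairs them. The oral month-3 count is zero on the plan's own fill schedule. At end of study, equal lateness would give 11-47% failing in the CAB-LA arm and 0.6-14% in the oral arm. Those sizes rest on assumed q and s, on independence, and on three refills that can count; the direction does not depend on the particular values.

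This is a should-fix. Item B is one of two adherence comparisons, has no named test, and sits beside persistence and possession-ratio analyses that can catch participants it misses. A reader might infer that the plan is tilted towards CAB-LA; on this item the tilt is the other way.

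**What to change.** 1. In Section 7, remove the between-arm comparison of the 7-day and >90-day percentages. Report each descriptively within its own arm.
2. In 6.2.7.1, drop oral item B at month 3.
3. If a date-based between-arm comparison is wanted at end of study, use one measure defined the same way in both arms, from the dates already needed for the possession ratio. PDC to a common cut-off, capped at 1, would serve. Pre-specify the cut-off, the test, and the days credited per fill and per injection; the documents give the schedule but no crediting rule.

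PDC should not be used at month 3, because with a 90-day first fill the oral value to day 90 is 100% by construction. Any clinical lateness threshold is for the sponsor to reconcile.

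Items 1 and 2 cost only wording. Item 3 needs modest programming and has three drawbacks that the SAP should acknowledge:

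- Counting uncovered time after stopping overlaps with persistence, which 6.2.2.1 defines as independent of adherence.
- Oral dispensing shows possession, while an injection date shows administration.
- Unequal visit frequency leaves a small residual difference: about 0.1-2.5 points with delays of 7-30 days, and about 3 points if half of late pick-ups at q = 10% exceed 90 days.

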6.2.8. Patient Reported Outcomes

6.2.8.1. Patient Reported Outcomes Set 1: PrEP Medication Satisfaction, PrEP-Related Stigma, Acceptability of Intervention Measure (AIM)

6.2.8.2. Patient Reported Outcomes Set 2: PrEP Acceptance, Intervention Appropriateness Measure (IAM)

6.2.8.3. Helpfulness of the education modules and Health Literacy Evaluation

6.2.9. Clinician Instruments

6.2.9.1. Baseline Provider Survey

6.2.9.1.1. Information About You and Your Patients

6.2.9.1.2. Acceptability of Intervention Measure (AIM)

6.2.9.1.3. Intervention Appropriateness Measure (IAM)

6.2.9.1.4. Feasibility of Intervention Measure (FIM)

6.2.9.1.5. Barriers and Facilitators for Implementation of Long-Acting Cabotegravir for PrEP

6.2.9.2. Follow-up Provider Survey

6.2.9.2.1. Information About You and Your Patients

6.2.9.2.2. Acceptability of Intervention Measure (AIM)

6.2.9.2.3. Intervention Appropriateness Measure (IAM)

6.2.9.2.4. Feasibility of Intervention Measure (FIM)

6.2.9.2.5. Barriers and Facilitators for Implementation of Long-Acting Cabotegravir for PrEP

6.3. Standard of Care Visits

6.3.1. The standard of care for patient visits will not be affected. The patients will only be given additional surveys to complete.

6.4. Follow-Up Visits

6.4.1. CAB-LA PrEP cohort: 2nd PrEP injection at month 1; follow-up labs and PrEP injections in months 3, 5, 7, 9, and 11.

6.4.2. Oral PrEP cohort: follow-up labs and prescription refills in months 3, 6, 9, and 12.

6.5. Switching between PrEP regimens

6.5.1. To be included in final data analysis, participants cannot switch between PrEP regimens before 6-months duration of initial PrEP.

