6.2.1. Baseline Patient Demographic Survey

6.2.2. Medication Persistence

6.2.2.1. Definition: Continue to take medicines over time independent of adherence to the PrEP medication regimen.

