6.2.3. Persistence Assessment CAB-LA

6.2.3.1. The proportion of participants who received at least one PrEP injection who remained on injectable PrEP or oral bridging at months 3 and 11 measured by the self-report assessment and validated with claims data.

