6.2.4. Persistence Assessment Oral PrEP

6.2.4.1. The proportion of participants who initiated oral PrEP who remained on oral PrEP at months 3 and 12 measured by the self-report assessment and validated with claims data period.

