6.10. Possible Participant Pathways

6.10.1. There will only be two observational cohort arms. Patients will either be placed into the injectable PrEP arm or the oral PrEP arm based on their baseline prescription.

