6.14. STATISTICAL ANALYSIS

6.14.1. Study Endpoints

6.14.1.1. Medication Adherence and Persistence

Medication persistence is defined as continuing to take PrEP over time independent of adherence to the medication regimen. The proportion of

patients reporting receipt of CAB-LA or oral PrEP at months 3 (early) and end of study (late) will be measured through patient questionnaires and validation protocols. Medication adherence is defined as taking PrEP in line with medical advice.

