You are treated with less respect than other people are. 
  Never  Less than once a year  A few times a year  A few times a month  At least once a week  Almost every day 	15
People act as if they're better than you. 
  Never  Less than once a year  A few times a year  A few times a month  At least once a week  Almost every day 	16
What do you think is the main reason for these experiences? (Select 1) 
  Your gender  Your sexual orientation  Your race  Your religion  Some aspect of your physical appearance  Your education or income level  Other: [Write in] 	17

End Message: Thank you for completing this survey!

Persistence Assessment

Activity Title: Are You Still Taking PrEP?

Activity Description: In this short survey, we'll ask you some questions about your PrEP journey and any challenges you may have encountered.

Activity:

1. Are you still getting PrEP medicine by an injection from your healthcare provider?

- Yes, I am taking PrEP ([branching logic to question 4](#))
- No, I stopped taking PrEP ([branching logic to question 2](#))

2. If you stopped taking PrEP, which of the following best describes the reason(s) why?

[Select up to 2]

- I no longer feel I needed to take PrEP ([branching logic to question 3 if selected](#))
- It was too difficult to take to take PrEP as prescribed with my lifestyle
- I felt I was being judged by others for taking PrEP
- I experienced side effects from taking PrEP

- I take too many medications
- There were too many appointments as part of my PrEP care
- I tested positive for HIV
- Other: [Fill in the blank]

3. Which of the following best describes why you no longer feel you need to take PrEP?

- I am no longer having sex
- I am in a monogamous relationship
- I am no longer using injectable drugs
- My partners and I are all regularly using condoms and getting tested for HIV
- Other: [Fill in the blank]

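### Section 6.5.1 removes early regimen switchers from the final analysis, so the primary persistence comparison is made in a set selected on an event tied to its own outcome

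*Combined protocol and SAP*

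**What the plan says.** The exclusion, in section 6.5.1: "To be included in final data analysis, participants cannot switch between PrEP regimens before 6-months duration of initial PrEP". It is not limited to a secondary or sensitivity analysis, and it does not say which outcomes it covers.

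The primary persistence measures have all-initiator denominators:
- CAB-LA (6.2.3.1) has: "The proportion of participants who received at least one PrEP injection who remained on injectable PrEP or oral bridging at months 3 and 11".
- Oral (6.2.4.1) has: "The proportion of participants who initiated oral PrEP who remained on oral PrEP at months 3 and 12".

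Section 6.10.1 fixes the arms at baseline: "Patients will either be placed into the injectable PrEP arm or the oral PrEP arm based on their baseline prescription". Section 7 compares "the proportion of participants reporting continued receipt of injections in the CAB-LA cohort" with the corresponding oral proportion at month 3 and end of study, by chi-square or Fisher's exact test.

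Two passages define persistence without naming a regimen. Section 6.2.2.1 has "Continue to take medicines over time independent of adherence to the PrEP medication regimen", and section 6.14.1.1 has "Medication persistence is defined as continuing to take PrEP over time independent of adherence to the medication regimen".

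The persistence surveys in Appendices B and C ask only about the starting route. In both, the only negative answer is "No, I stopped taking PrEP".

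**The concern.** Inclusion depends on behaviour in the six months after PrEP starts, and that behaviour is close to the endpoint itself. If persistence means staying on the starting modality, early switchers are failures, and removing them takes failures out of both numerator and denominator accounting. If it means staying on any PrEP, switchers still on PrEP are successes and the rule removes successes.

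The term for a switch between regimens is also undefined. Read literally, it could catch a change from FTC/TDF to FTC/TAF, which remains oral PrEP under 6.2.4.1, or oral bridging, which 6.2.3.1 counts as persistent.

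At stake is the co-primary contrast. The rule can shrink the difference, enlarge it or leave it nearly unchanged, depending on which arm switches more and which definition applies. A reader of the results could not tell which had happened. With 35 people in the oral arm, a few exclusions matter.

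**Working it through.** **1. How the rule treats each path (arm-specific definition, no return to the initial regimen)**

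| Path | Month 3 status | End-of-study status | Under 6.5.1 |
|---|---|---|---|
| Modality switch at month 2 | failure | failure | deleted |
| Modality switch at month 5 | persistent | failure | deleted |
| Modality switch at month 7 | persistent | failure | kept |
| Complete stop at month 5 | persistent | failure | kept |

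At end of study, the rule can only raise an arm's persistence. At month 3 its effect is mixed.

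**2. The plan's own figure**

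Inputs (section 7, Sample Size): proportions 0.90 and 0.65, labelled adherence; n = 70 and 35. The Wald interval is (p1 − p2) ± 1.96 × √[p1(1 − p1)/n1 + p2(1 − p2)/n2]:

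0.25 ± 1.96 × √(0.09/70 + 0.2275/35) = 0.25 ± 1.96 × 0.0882 = 0.25 ± 0.1729, or 0.0771 to 0.4229.

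This reproduces the stated interval. It uses all 70 and 35, with no allowance for people removed by 6.5.1.

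**3. Effect of dropping early switchers**

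The documents give no switching rate and no planning value for persistence. As an assumption, the adherence proportions are borrowed: 0.90 × 70 = 63, and 0.65 × 35 = 22.75, taken as 23. Who switches is also assumed. The intervals use the same Wald formula; p-values are two-sided Fisher.

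| End-of-study case | CAB-LA | Oral | Difference | 95% CI | Fisher p |
|---|---|---|---|---|---|
| All initiators | 63/70 | 23/35 | 0.243 | 0.071 to 0.415 | 0.0057 |
| (a) 4 oral failures dropped | 63/70 | 23/31 | 0.158 | −0.011 to 0.327 | 0.065 |
| (a′) 3 oral failures dropped | 63/70 | 23/32 | 0.181 | 0.010 to 0.352 | 0.037 |
| (b) 4 CAB-LA failures dropped | 63/66 | 23/35 | 0.297 | 0.132 to 0.462 | 0.0001 |
| (c) 2 failures dropped per arm | 63/68 | 23/33 | 0.230 | 0.061 to 0.398 | 0.0053 |

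In case (a) the chi-square test without continuity correction gives p = 0.039. The smallest expected count there is 4.6, which favours Fisher.

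**4. The same people under the any-PrEP reading**

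(d) If the four oral switchers in (a) are still on PrEP, all initiators give 63/70 versus 27/35: 0.900 − 0.771 = 0.129 (CI −0.027 to 0.284). The rule still gives 0.158, now too large rather than too small.

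**5. Month 3**

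(e) If 30/35 oral participants are persistent at month 3 (0.857) and four of them switch in months 4 to 6, the rule gives 26/31 (0.839). Here it lowers the arm's figure slightly.

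**6. General form**

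With early-switch share s and true proportion p, the estimate after exclusion is p/(1 − s) if switchers are failures, and (p − s)/(1 − s) if they are successes. With 0.90 and 0.65 (true difference 0.250):
- Failures, s = 0 in CAB-LA and 20% in oral: 0.900 − 0.65/0.80 = 0.088.
- Failures, s = 10% in CAB-LA and 0 in oral: 0.90/0.90 − 0.650 = 0.350.
- Successes, s = 0 in CAB-LA and 20% in oral: 0.900 − 0.45/0.80 = 0.338.

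The sign of the bias changes with the arm that switches and with the definition.

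**The case against.** - **The direction is partly known.** Under the arm-specific definition, dropping switchers who have not returned can only raise that arm's end-of-study persistence. This stands; what cannot be determined is the net effect on the between-arm difference.
- **The any-PrEP reading is weaker.** Sections 6.2.3.1 and 6.2.4.1 make the general definition specific by arm, and the planned test and both surveys follow the starting route. This is fair, so case (d) is secondary. Still, the general wording appears twice and should be reconciled.
- **A switch naturally means crossing arms.** With only two arms in 6.10.1 and bridging counted as persistent in 6.2.3.1, that is the likely intent. It still needs stating, above all for changes between oral products.
- **Section 6.6.1 is a separate discontinuation rule.** It requires more than three consecutive missed months, so nobody could be deemed discontinued by month 3, and a switcher still on PrEP has arguably not discontinued. The month 3 statements above apply to the self-report measure in section 7; 6.6.1 must be reconciled with it.
- **The illustration is finely balanced.** Case (a) needs 4 of 12 oral failures, and no CAB-LA failures, to be early switchers. With three oral switchers the interval excludes zero. With four oral and one CAB-LA (63/69 versus 23/31) it is 0.003 to 0.339, Fisher p = 0.031. Case (c) shows almost no change.
- **Switching may be rare.** Possibly, but the plan gives no rate, and the Appendix C acceptance survey asks about choosing to switch to injections.

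These points narrow the claim about size and direction. None supplies an all-initiator analysis or limits the scope of 6.5.1.

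**Conclusion.** The concern holds and must be fixed. Section 6.5.1 and the denominators in 6.2.3.1 and 6.2.4.1 cannot both be followed, and the exclusion depends on an event that is itself a form of the primary outcome. No other section repairs this.

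In the illustrations, four exclusions in one arm move a 24-point end-of-study difference to 16 or to 30 points, while two per arm leave it at 23. These sizes rest on assumed counts, on adherence proportions standing in for persistence, and on dropped switchers being failures under the arm-specific definition. They show what the rule can do, not what it will do. The conflict between the sections rests on the text alone.

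**What to change.** 1. Replace the 6.5.1 exclusion with a primary analysis of all initiators, grouped by baseline prescription as in 6.10.1.
2. For the analysis, define a switch as a change between injectable and oral modality, so that FTC/TDF to FTC/TAF changes and oral bridging remain persistent, in line with 6.2.3.1 and 6.2.4.1. State how the dispensing record separates bridging from a switch.
3. Count a modality switch before a landmark as not persistent on the initial regimen at that landmark, and state how a return to the initial regimen is scored.
4. Report being on any PrEP at the landmark as a second version. Reconcile 6.2.2.1 and 6.14.1.1 with 6.2.3.1 and 6.2.4.1 on which version is primary, and state how 6.6.1 relates to both.
5. Classify switchers from the planned claims data and the clinic pharmacy's dispensing records (5.1.3), supported by the EHR, already listed as a primary-endpoint source. The closed survey items cannot do this, and the free-text option is not reliable for it.
6. Keep the no-early-switch set as a sensitivity analysis only, say which outcomes it covers, and report the number excluded by arm.

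The cost is analysis-plan wording, one extra table and the work of classifying switchers from records already planned. The arm with more switching may show less favourable persistence on its initial regimen.
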